1.1 Primary Objectives

- 1.1.1 To determine the maximum tolerated dose (MTD) or recommended phase 2 dose (RP2D) of combination decitabine and ipilimumab for relapsed or refractory MDS or relapsed or refractory AML in patients who are post allogeneic hematopoietic stem cell transplant (allo-HCT).
- 1.1.2 To determine the MTD or RP2D of combination decitabine and ipilimumab for relapsed or refractory MDS or relapsed or refractory AML in patients who are transplant naive.

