AML is a disease of the elderly with a median age of diagnosis of 67 years (SEER 2008-2012). Chemotherapy resistance and disease relapse are the primary challenges affecting the majority of patients in the treatment of acute leukemia. For patients less than 60 years of age, traditional induction chemotherapy with combination anthracycline and cytarabine results in CR rates of 50-70% [11]. Despite achieving remission, a significant number of younger patients with AML with poor risk features at diagnosis will be refractory to induction therapy or ultimately relapse after initial response to induction chemotherapy. Poor risk features include antecedent hematological disorder, adverse cytogenetic features, and adverse molecular mutations [12]. Disease relapse remains the primary cause of treatment failure. Elderly patients with AML have a poor prognosis due to increased disease resistance to standard intensive chemotherapy regimens and relatively decreased tolerance to these agents [13]. There is no identified optimal treatment strategy for elderly patients who are not candidates for allo-HCT, which remains the only curative option in this setting but is actually applied to only a small number of patients. Less intensive and therefore better-tolerated regimens include low-dose cytarabine and hypomethylating agents. Azacitidine is approved for the treatment of MDS and for patients with AML with low blast count (20-30% bone marrow blasts). Although approved in the United States for the treatment of MDS including patients with 20-30% bone marrow blasts and in Europe for the treatment of AML, decitabine continues to be used off-label given its anti-leukemic activity and tolerability. In a multicenter phase 2 study, elderly patients with untreated AML received decitabine 20 mg/m² intravenously for 5 consecutive days every 28 days [14]. Results from this study showed a CR rate of 24%, a median OS of 7.7 months and a 30-day mortality rate of 7% [14]. A large, randomized phase III study for patients 65 years and older with untreated AML comparing decitabine to supportive care and cytarabine demonstrated a CR plus CRp rate of 17.8% versus 7.8%, respectively [15]. Hence, hypomethylating agents such as decitabine are a reasonable anti-leukemic agent given its tolerability but its anti-leukemic activity and survival benefits are limited as a single agent. The development of novel and effective non-intensive therapeutic strategies for elderly AML patients remain an unmet need.

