3. PATIENT SELECTION

3.1 Eligibility Criteria

3.1.1 Age 18 and older.

3.1.2 Subjects with evidence of AML or MDS that meet at least one of the following criteria:

- Relapsed AML: evidence of $\geq 5\%$ blasts in the bone marrow; or reappearance of blasts in the peripheral blood; or development of

extramedullary disease (according to 2003 IWG criteria [6]) who relapse after:

- Allogeneic hematopoietic stem cell transplant, or
- After one cycle of standard cytotoxic chemotherapy or two cycles of any hypomethylating agent-based therapy
- Refractory AML: ≤ 2 prior induction regimens (example: patients who receive 7+3 followed by 5+2 would count as one induction regimen) or a minimum of two cycles of any hypomethylating agent-based therapy.
- Treatment-naive AML: must be 75 years and older with *de novo* or *secondary* AML to be considered eligible
- Relapsed MDS: disease recurrence after CR, PR or hematologic improvement with bone marrow blasts $\geq 5\%$ who relapse after:
 - Allogeneic hematopoietic stem cell transplant, or
 - After four cycles of any hypomethylating agent-based therapy
- Refractory MDS: disease progression at any time after initiation of hypomethylating agent treatment or persistent bone marrow blasts $\geq 5\%$ despite a minimum of four cycles of hypomethylating agent therapy.
- Untreated or previously treated therapy- related or secondary MDS

- 3.1.3 Allowed prior allogeneic hematopoietic stem cell transplantation (allo-HCT) regardless of stem cell source. Patients must be at least 3 months post allo-HCT (at time of treatment start). Mismatched transplantations would be allowed.
- 3.1.4 Patients must be off systemic immunosuppressive medications >2 weeks prior to treatment start. If patients are on systemic corticosteroids and must be on a dose of prednisone 5 mg/day or less (or equivalent), then patients must be on this reduced dose for >1 week prior to treatment start. Topical steroids are allowed
- 3.1.5 If post allo-HCT, then patient must have baseline donor T cell chimerism of $\geq 20\%$ (from peripheral blood). Evaluation can be made within 4 weeks of treatment start.
- 3.1.6 No limitations on prior therapies.
- 3.1.7 ECOG performance status ≤ 2 (see [Appendix A](#))
- 3.1.8 Participants must have normal organ as defined below:
 - Total bilirubin $\leq 1.5 \times$ local institutional upper limit of normal (ULN)

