11.1.2 Progression-Free Survival

Overall Survival: Overall Survival (OS) is defined as the time from time of registration to death due to any cause, or censored at date last known alive. We will evaluate for survival differences among patients that respond based on transplant status.

Progression-Free Survival: Progression-Free Survival (PFS) is defined as the time from time of registration to the earlier of progression or death due to any cause. Participants alive without disease progression are censored at date of last disease evaluation.

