13. STATISTICAL CONSIDERATIONS

13.1 Study Design/Endpoints

This is an open-label phase 1 study using a standard 3+3 dose-escalation design with planned dose escalation of ipilimumab in combination with decitabine, to define the safety profile and MTD (RP2D) in patients with R/R MDSAML with and without previous allogeneic HSCT. Two arms are planned. Arm A will include a cohort of patients who are post-transplant (patients who were transplanted by allogeneic HSCT at any time). Arm B will include a cohort of patients who are transplant naive (patients who never received allo-HSCT). Both cohorts will be tested at three different ipilimumab dose levels (dose level 0 (starting dose; first dose level): 3 mg/kg, dose level 1: 5 mg/kg, and dose level 2: 10 mg/kg). Three to six patients will be evaluated at each dose level per arm.

Please see section 5.1 for details on patient enrollment. We will demonstrate safety in the first dose level in patients on Arm B prior to enrolling patients onto Arm A. After safety is demonstrated at this first dose level, enrollment can then occur simultaneously without further delay or observation period. A dose de-escalation level (-1) will be allowed with ipilimumab at 1 mg/kg. Arm A does not need to complete dose escalation before Arm B if Arm B is able to move to dose-expansion; and vice versa. In the event that 0 of 3 patients in a dose level experience a DLT, the dose level may still be expanded to 6 evaluable patients based on observed toxicity at the current dose level at the discretion of the overall PI to capture patient safety prior to expanding.

Dose escalation will follow a standard 3+3 design exploring 3 dose levels of ipilimumab (starting at dose level 0, at 3 mg/kg) with decitabine (20 mg/m² daily x 5 consecutive doses). We will escalate to next dose cohort if 0/3 or 1/6 participants have a DLT during the first two cycles of combination therapy (cycles 1+2; first 8 weeks of combination therapy). If the rate of dose limiting toxicity (DLT) exceeds 30%, it is less likely that the dose of ipilimumab will be

dose-escalated. The table below provides the probability that the dose will be escalated, i.e., that 0 in 3 or 1 in 6 patients experience a DLT, given the true but unknown rate of DLT.

	True but unknown probability of DLT				
	0.10	0.20	0.30	0.40	0.50
P(escalate)	0.91	0.71	0.49	0.31	0.17

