Additionally, efficacy of decitabine plus ipilimumab will be assessed for the total number of patients enrolled at the MTD/RP2D for each arm. Anti-leukemic activity will be described in terms of best overall response rate (for AML, to include CR+CRI; for MDS, to include CR+marrow CR+PR+HI). Assuming 6 patients are enrolled at the MTD/RP2D from the dose escalation phase and an additional 6 patients for the cohort expansion, the 90% exact binomial confidence interval will be within +/- 25%. Assuming 6 patients are enrolled at the MTD/RP2D from the dose escalation phase and an additional 12 patients from the cohort expansion, the 90% exact binomial confidence interval will be within +/- 21%.

Overall survival (OS) is defined as the time from registration to death due to any cause or censored at the date last known alive. Progression-free survival (PFS) is defined as the time from registration to the earlier of progression or death due to any cause. Survival outcomes will be

estimated by the method of Kaplan and Meier. OS and PFS will be evaluated within each arm.

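### Section 3.1.2 admits untreated AML and MDS, but the objectives and Section 13.1 name relapsed/refractory disease and no analysis separates the two, so Arm B's response rate does not estimate the stated population

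*Combined protocol and SAP*

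**What the plan says.** **Stated population.** Objective 1.1.1 seeks the MTD or RP2D "for relapsed or refractory MDS or relapsed or refractory AML in patients who are post allogeneic hematopoietic stem cell transplant". Objective 1.1.2 seeks it for "relapsed or refractory MDS or relapsed or refractory AML in patients who are transplant naive". The introduction to Section 1 describes the same population, and Section 13.1 sets out to define safety and the MTD "in patients with R/R MDSAML with and without previous allogeneic HSCT".

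**Admitted population.** Section 3.1.2 lists relapsed and refractory AML and MDS. It then adds "Treatment-naive AML: must be 75 years and older" (de novo or secondary) and "Untreated or previously treated therapy- related or secondary MDS". Neither group is capped.

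**Analysis.** Section 13.1 states that "efficacy of decitabine plus ipilimumab will be assessed for the total number of patients enrolled at the MTD/RP2D for each arm", and that OS and PFS are evaluated within each arm. Section 13.5 makes a patient evaluable for response after one ipilimumab dose, with no condition on prior treatment. AML and MDS keep separate response definitions, but nothing is split by prior treatment. No text follows the heading of Section 13.3 (Stratification Factors). Section 11.1.2 adds: "We will evaluate for survival differences among patients that respond based on transplant status".

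**The concern.** The population that the objectives name is not the population that the analysis describes. A patient who has never been treated has had no allograft, so untreated patients enter Arm B (transplant naive), while Arm A is essentially relapse after transplant. The mixture therefore sits in one arm.

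Two things are at stake. First, Arm B's response rate would be read as activity in R/R disease, and Section 1 makes preliminary efficacy one of the conditions for a phase 2 trial. Some of those responses could come from patients receiving decitabine as first-line therapy, where the protocol itself reports single-agent activity. Second, any contrast by transplant status would also be a contrast by line of therapy.

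The mismatch touches the primary objective in wording too: an Arm B MTD/RP2D labelled R/R may rest partly on untreated patients. Nothing in the documents shows that line of therapy changes the DLT rate, so that part is a labelling problem only.

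**Working it through.** **1. The plan's own precision figures.** Section 13.1 says the 90% exact binomial interval is within +/-25% for 6 + 6 = 12 patients and within +/-21% for 6 + 12 = 18. Taking the Clopper-Pearson 90% interval for every possible number of responders, the largest half-width is 25.5 points at n = 12 and 20.9 points at n = 18. The stated figures reproduce as half-widths and are not in question.

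**2. Inputs for the mixture.**

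- Untreated AML on decitabine alone, from Section 2.1. The phase 2 study: "Results from this study showed a CR rate of 24%, a median OS of 7.7 months". The phase III study: CR plus CRp of 17.8%. Section 2.3 gives a front-line CR range of 18-25%, which agrees.
- Untreated share of Arm B: not in the documents. Assumed 6 or 9 of 18.
- Decitabine-alone response in R/R patients: not in the documents. Assumed 10%, varied from 5% to 20%.
- Ipilimumab effect: set to zero, to isolate what the mixture does by itself.

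**3. Formula.** With k untreated patients of 18:

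- pooled rate = (k x p_untreated + (18 - k) x p_RR) / 18
- shift = k x (p_untreated - p_RR) / 18

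**4. Results, as pooled rate (shift in points).**

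| Assumed R/R rate | 6 of 18, untreated 17.8% | 6 of 18, untreated 24% | 9 of 18, untreated 17.8% | 9 of 18, untreated 24% |
|---|---|---|---|---|
| 5% | 9.3% (+4.3) | 11.3% (+6.3) | 11.4% (+6.4) | 14.5% (+9.5) |
| 10% | 12.6% (+2.6) | 14.7% (+4.7) | 13.9% (+3.9) | 17.0% (+7.0) |
| 15% | 15.9% (+0.9) | 18.0% (+3.0) | 16.4% (+1.4) | 19.5% (+4.5) |
| 20% | 19.3% (-0.7) | 21.3% (+1.3) | 18.9% (-1.1) | 22.0% (+2.0) |

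Worked example: (6 x 0.24 + 12 x 0.10) / 18 = 2.64 / 18 = 14.7%.

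In counts, six untreated AML patients at 24% are expected to give 6 x 0.24 = 1.4 responders on decitabine alone. The chance of at least one is 1 - 0.76^6 = 0.81.

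**5. Would the lead-in remove decitabine-only responses?** No. Section 11.1 counts best response from the start of treatment, and the decitabine-only priming cycle is part of treatment. The end-of-lead-in marrow is a research aspirate (Section 10.1, footnote j; Section 10.2, footnote 7), so there is no formal response assessment before ipilimumab.

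**6. Why the MDS figure is left out.** Section 2.1 reports 17 + 15 + 18 = 50 of 99 MDS patients improved on decitabine (50.5%). It does not say that they were untreated, nor that they had therapy-related or secondary MDS. That total also includes hematologic improvement, so it is a different endpoint from CR + CRi. It cannot serve as the rate for the untreated patients admitted here.

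**7. Survival.** The documents give no figures from which a shift in PFS or OS could be calculated. The point there is only that the population is mixed.

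**The case against.** The strongest reply is that this is a phase 1 dose-finding trial. Response and survival are secondary and descriptive, with no efficacy threshold, no historical control and no power claim. Section 13.5 says the focus is safety and the RP2D. Enrolling older untreated AML patients fits the unmet need described in Section 2.1, and a single-arm combination cannot separate ipilimumab from decitabine in R/R patients either. A shift of 3 to 7 points also lies well inside the plan's +/-21. All of this stands and limits the consequence. It does not remove the mismatch: the rate still describes a population other than the one named, and more precision would not correct that.

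A reader might infer that Arm B's activity *is* inflated, perhaps by as much as 20 points. The documents do not support that. The untreated share and the R/R rate are both unknown, the shift can be zero or slightly negative, and a figure near 20 points needs the 50.5% MDS rate to be treated as a rate in untreated patients.

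A reader might also infer that the trial plans to test whether alloreactivity is needed by comparing response between arms. It does not. Section 2.4 says only that this is unknown. Section 11.1.2 plans a look at survival among responders, Section 13 gives that look no specified test, and transplant history would confound it in any case. Line of therapy is an additional and avoidable confounder.

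The empty Section 13.3 is weak evidence in a nonrandomised trial, and nothing here depends on it.

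**Conclusion.** The concern holds as a mismatch between the eligible and the stated populations, carried into the analysis. Followed as written, Arm B's response, PFS and OS will not estimate outcomes in R/R disease, and the response rate *can* be raised by first-line decitabine responses.

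The amount cannot be determined from the documents. It is about 3 to 7 points under the assumptions of a 10% R/R rate, 6 to 9 of 18 patients untreated, no ipilimumab effect, and the protocol's untreated AML rates of 17.8% and 24%. It grows if the R/R rate is lower and vanishes if that rate is near the first-line one. The escalation rules, sample size and stated precision are not in error. This should be corrected, but it does not threaten the dose-finding design.

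**What to change.** 1. Make the population wording in Sections 1.1 and 13.1 agree with Section 3.1.2, or the reverse.
2. In Sections 13.1 and 13.5, report best overall response (AML and MDS by their own definitions), remission duration, PFS and OS in each arm separately for R/R and not-R/R patients.
3. Define the not-R/R group to include previously treated therapy-related or secondary MDS that meets no relapsed or refractory criterion. Section 3.1.2 admits such patients, and a simple treated/untreated split would leave them unplaced.
4. State that the R/R subset is the estimate that answers the stated objectives.
5. Limit any descriptive comparison by transplant status to R/R patients.

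**Cost.** Text changes only; prior treatment is already established for eligibility, and the DLT rules and sample size are unchanged. The price is precision: the largest 90% exact half-width is about 21 points at 18 patients, 25 at 12 R/R patients and 29 at 9. At an assumed 10% rate, 12 R/R patients yield about 12 x 0.10 = 1.2 responders, so a survival comparison among R/R responders would carry very little information and should be presented that way.

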3.2 Exclusion Criteria

3.2.1 Participants who have had chemotherapy or radiotherapy within 2 weeks prior to treatment start or those who have not recovered from adverse events due to agents administered more than 2 weeks prior to treatment start.

- Hydroxyurea is allowed for symptomatic leukocytosis if clinically necessary. A total white blood cell (WBC) count $< 25 \times 10^9/L$ prior to first dose of decitabine on trial is required. Prior leukapheresis and/or prior or concurrent treatment with hydroxyurea to achieve this level are allowed.
- Ongoing concurrent hormonal therapy is allowed

3.2.2 Participants with known CNS involvement with leukemia or who are receiving intrathecal chemotherapy for active CNS leukemia

- Those with a history of CNS involvement that has been completely treated and those who require intrathecal chemotherapy prophylaxis are eligible in the expansion cohorts

3.2.3 Prior HMA therapy is allowed, however this study *excludes* patients with progression or relapse that occur while receiving HMA-based therapy within 12 weeks prior to treatment start on study.

Disease progression is defined as either: (1) patients with prior MDS who progress to AML (defined by the presence of $\geq 20\%$ blasts in peripheral blood or bone marrow) on HMA-based therapy; OR (2) patients with AML with evidence of progressive disease according to ELN 2017 criteria (Appendix H for details) (e.g.

>50% increase in marrow blasts over baseline or >50% increase in peripheral blasts to > 25 x10⁹/L (>25,000/uL) (in absence of differentiation syndrome)).

(Note: Patients who relapse post-transplant who received HMA treatment prior to transplant are eligible for study.)

- 3.2.4 Donor lymphocyte infusion within 8 weeks prior to treatment start if post-transplant.
- 3.2.5 For patients that are post-transplant, ineligible patients include those with a history of overall grade III or IV (severe) acute GVHD at any time even if resolved.
- 3.2.6 Patients with a history of prior treatment with anti-CTLA-4 antibody, anti-PD 1 antibody, or anti- PDL1 antibody.
- 3.2.7 Participants who are receiving any other investigational agents.
- 3.2.8 Participants with known CNS involvement with leukemia or who are receiving intrathecal chemotherapy that is either prophylactic or therapeutic. History of CNS involvement that has been completely treated (no longer receiving intrathecal chemotherapy) will be allowed.
- 3.2.9 Uncontrolled intercurrent illness including, but not limited to, ongoing or active infection, symptomatic congestive heart failure, unstable angina pectoris, cardiac arrhythmia, or psychiatric illness/social situations that would limit compliance with study requirements. Any other prior or ongoing condition, in the opinion of the investigator, that could adversely affect the safety of the patient or impair the assessment of study results. As patients with AML and MDS are prone to infections, if patients are actively being treated with appropriate antibiotics or antifungal therapy with clinical evidence of infection control, then they will be considered eligible for study.
- 3.2.10 **Autoimmune disease:** Patients who are not eligible include those with a history of inflammatory bowel disease, including ulcerative colitis and Crohn's Disease, are excluded from this study, as are patients with a history of symptomatic disease (e.g., rheumatoid arthritis, systemic progressive sclerosis [scleroderma], systemic lupus erythematosus, autoimmune vasculitis [e.g., Wegener's Granulomatosis]); CNS or motor neuropathy considered of autoimmune origin (e.g., Guillain-Barre Syndrome and Myasthenia Gravis, multiple sclerosis). Patients with a history of autoimmune disease (specifically including: diabetes mellitus, vitiligo, hashimoto's thyroiditis) who are asymptomatic, do not require immune suppression or steroids, and do not have threatened vital organ function from these conditions may be considered after discussion with the PI

- 3.2.11 No concurrent active malignancies are allowed on study for ≥ 2 years prior to treatment start with the exception of currently treated basal cell or squamous cell carcinoma of the skin, or carcinoma in-situ of the cervix or breast.
- 3.2.12 Patients with known active hepatitis B virus (HBV) infection should be excluded because of potential effects on immune function and/or drug interactions. However, if a patient has HBV history with an undetectable HBV load by polymerase chain reaction (PCR), no liver-related complications, and is on definitive HBV therapy, then he/she would be eligible for study.
- 3.2.13 Patients with known active hepatitis C virus (HCV) infection. Patients with a history of HCV infection who received definitive therapy and has an undetectable viral load by PCR would be eligible.
- 3.2.14 Pregnant women are excluded from this study because ipilimumab has the potential for teratogenic or abortifacient effects. Because there is an unknown but potential risk for adverse events in nursing infants secondary to treatment of the mother with ipilimumab, breastfeeding should be discontinued if the mother is treated with ipilimumab. These potential risks may also apply to decitabine.

3.3 Pregnancy

The effects of ipilimumab on the developing human fetus are unknown. For this reason and because immunotherapy agents as well as decitabine are known to be teratogenic, women of child-bearing potential and men must agree to use adequate contraception (hormonal or barrier method of birth control; abstinence) prior to study entry and for the duration of study participation. Should a woman become pregnant or suspect she is pregnant while she or her partner is participating in this study, she should inform her treating physician immediately. Men treated or enrolled on this protocol must also agree to use adequate contraception prior to the study, for the duration of study participation, and 4 months after study drug administration.

Sexually active women of child-bearing potential (WOCBP) must use an effective method of birth control during the course of the study, in a manner such that risk of failure is minimized. Before enrolling WOCBP in this clinical study, the investigator must review the guideline about study participation for WOCBP which can be found in the GCP Manual for Investigators. The topics include the following:

- General Information
- Informed Consent Form
- Pregnancy Prevention Information Sheet
- Drug Interactions with Hormonal Contraceptives
- Contraceptives in Current Use
- Guidelines for the Follow-up of a Reported Pregnancy.

Before study enrollment, WOCBP must be advised of the importance of avoiding pregnancy during study participation and the potential risk factors for an unintentional pregnancy. The subject must sign an informed consent form documenting this discussion.

All WOCBP MUST have a negative serum quantitative pregnancy test within 72 hours of receiving treatment on study. The minimum sensitivity of the pregnancy test must be 25 IU/L or equivalent units of HCG. If the pregnancy test is positive, the subject must not receive ipilimumab and must not be enrolled in the study.

In addition, all WOCBP should be instructed to contact the investigator immediately if they suspect they might be pregnant (e.g., missed or late menstrual period) at any time during study participation.

If, following initiation of the investigational product, it is subsequently discovered that a study subject is pregnant or may have been pregnant at the time of investigational product exposure, including during at least 6 half-lives after product administration, the investigational product will be permanently discontinued in an appropriate manner (e.g., dose tapering if necessary for subject safety). Pregnancies should be reported directly to CTEP through the Adverse Event Reporting System (AERS) and must also be accompanied by the Pregnancy Information Form

Protocol-required procedures for study discontinuation and follow-up must be performed on the subject unless contraindicated by pregnancy (e.g., X-ray studies). Other appropriate pregnancy follow-up procedures should be considered if indicated. In addition, the investigator must report and follow-up on information regarding the course of the pregnancy, including perinatal and neonatal outcome. Infants should be followed for a minimum of 8 weeks.

